Moreover, very few randomized clinical trials (RCTs) are powered to study side effects when comparing substances, and even large RCTs may be too small to reveal rare side effects. It seems difficult to compare safety data from trial to trial because there is no standardized definition of bleeding. One prospective study collecting data from the electronic health record at two institutions concluded that using of enoxaparin for VTE prophylaxis following THA and TKA was associated with a lower rate of the primary outcome (any postoperative bleeding) compared with the use of rivaroxaban in a similar cohort of patients. However, it was a retrospective investigation with many limitations can be argued with regard to selection and change in practice guideline during the study period.

Finally, there is lack of literature data that define rivaroxaban as orthopedic postoperative thromboprophylactic agent rather than well-known indications (hip and knee replacements). It also is not plausible to accurately compare safety data with other injectable anticoagulants.

Aim of the work

The main objective is to reduce the incidence of venous thromboembolism (VTE) in orthopedic postoperative patients based on the potential benefit of using rivaroxaban as a monotherapy.

It is around efficacy and safety evaluation of using rivaroxaban as a monotherapy prophylactic agent in patients undergoing orthopedic surgeries taking into the account the reliable selection of patients most benefit.

Answering questions about additional cost benefit from the perspective of the cost-effective analysis on extrapolating the results emerged to our university teaching hospital setting are going to be evaluating as well.

Methodology

Study design and randomization

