The primary efficacy outcomes are the composite of any deep-vein thrombosis, nonfatal pulmonary embolism, or death up to 30 days. The main secondary efficacy outcome is major venous thromboembolism, which is defined as the composite of proximal deep-vein thrombosis, nonfatal pulmonary embolism, or death from venous thromboembolism.

The main safety outcome is the incidence of major bleeding beginning after the first dose of the study drug and up to 2 days after the last dose of the study drug (on-treatment period). Major bleeding is defined as bleeding that is fatal, occurs in a critical organ (e.g., retroperitoneal, intracranial, intraocular, and intraspinal bleeding), or requires reoperation or extra surgical-site bleeding that was clinically overt and is associated with a fall in the hemoglobin level of at least 2 g per deciliter or that requires transfusion of 2 or more units of whole blood or packed cells. Other safety outcomes include any on-treatment bleeding, any on-treatment non- major

bleeding, hemorrhagic wound complications (a composite of excessive wound hematoma and reported surgical-site bleeding), any bleeding that starts after the first oral dose of rivaroxaban and ended up to 2 days after the last dose is administered, adverse events, and death.

Validated clinical prediction rule is recommended to estimate pretest probability of venous thromboembolism. Duplex ultrasonography is the preferred test to diagnose DVT [7]. Many prediction scales are available like *Wells Clinical Models for Evaluating the Pretest Probability of VTE*.

Symptoms and signs of DVT may include unilateral leg swelling, pain in the affected leg, calf tenderness in affected leg, increased leg warmth, erythema of affected leg, or a “palpable cord” may be felt in the affected leg.

Regarding PE, diagnosis is suspected in patients with dyspnea, tachypnea, pleuritic chest pain, cough, and/or fever. Diagnosis begins with initial risk stratification based on presence of shock or persistent hypotension to identify patients at high risk of early mortality.

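### The 2 g/dL hemoglobin criterion, and probably the 2-unit transfusion criterion, covers only bleeding outside the surgical site, so serious wound bleeds managed without reoperation cannot be compared between arms

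*Combined protocol and SAP*

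**What the plan says.** All of this stands in the protocol under Outcome measure and follow up, unless another section is named.

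- **Main safety outcome.** "The main safety outcome is the incidence of major bleeding beginning after the first dose of the study drug", with the window closing 2 days after the last dose.
- **Criteria that apply at any site.** "Major bleeding is defined as bleeding that is fatal, occurs in a critical organ", or leads to reoperation.
- **Criteria tied to a site.** The sentence continues with "extra surgical-site bleeding that was clinically overt and is associated with a fall in the hemoglobin level of at least 2 g per deciliter". It ends "or that requires transfusion of 2 or more units of whole blood or packed cells".
- **Other bleeding outcomes.** "Other safety outcomes include any on-treatment bleeding, any on-treatment non- major" bleeding, and "hemorrhagic wound complications (a composite of excessive wound hematoma and reported surgical-site bleeding". Bleeding after the first oral rivaroxaban dose, adverse events and death are also listed.
- **Laboratory data.** The section recommends baseline serum creatinine and platelet count, then platelet monitoring. It gives no hemoglobin schedule or reference value.
- **Start of treatment** (Study design and randomization). Rivaroxaban starts 6 to 10 hours after surgery. Table 1 gives enoxaparin a first dose 9 to 15 hours before surgery, and also cites guidance for a start at least 12 hours before or at least 12 hours after.

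**The concern.** Every patient has orthopedic surgery and every patient receives an anticoagulant, so the operated site is an obvious place for a drug difference in bleeding to appear. Yet the two measurable severity thresholds seem to apply everywhere except there. A wound bleed with a large hemoglobin fall, treated without reoperation, is filed as non-major beside wound bleeds that needed nothing.

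Safety is a stated aim. The protocol's background says that safety is hard to compare across trials because "there is no standardized definition of bleeding". If the arms differed in serious wound bleeding managed without reoperation, the main safety outcome would not show it, and the remaining rows would show it only mixed with milder events.

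**Working it through.** The documents state no bleeding rate, effect size or power, so there is no figure of theirs to reproduce. The check is a reading of the definition, followed by simple arithmetic on scale.

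**1. Which bleeds each criterion covers.** In the natural grammar, both closing clauses (overt with a hemoglobin fall; requiring transfusion) describe bleeding outside the surgical site. A second reading takes the transfusion clause as parallel to the opening criteria, so that it applies at any site. The hemoglobin clause stays tied to bleeding outside the surgical site either way.

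| Surgical-site bleed | Natural reading | Alternative reading |
|---|---|---|
| Fatal, in a critical organ, or reoperated | major | major |
| Overt, fall of 2 g/dL or more, fewer than 2 units, none of the above | non-major | non-major |
| Overt, 2 or more units, none of the first-row criteria | non-major | major |
| Reported, neither threshold met | non-major | non-major |

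Outside the surgical site, the second and third rows would be major.

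**2. Whether another outcome separates them.** Any on-treatment bleeding and non-major bleeding carry no grading. The wound composite requires a hematoma to be excessive, which is not defined, and requires surgical-site bleeding only to be reported. None uses hemoglobin or transfusion. The second and fourth rows, and the third on the natural reading, therefore count alike.

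**3. Whether the existing window suits wound bleeding.** It opens at the first dose. With a preoperative enoxaparin start, that arm's window opens between 9 + 6 = 15 and 15 + 10 = 25 hours earlier, relative to surgery, than the rivaroxaban window, plus the length of the operation. It would contain the operation itself; the rivaroxaban window would not. If the thresholds were extended to the wound on this window, operative loss could count in one arm only.

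**4. Scale.** Input: at least 100 patients in two groups (Study design and randomization). Assumption: 1:1, so 50 per arm. One reclassified event changes an arm's rate by 1/50 = 2 percentage points.

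For context, with assumed rates p that do not come from the documents, expected events per arm are 50p. The chance of no event in 100 patients is (1 − p)^100, taking the same p in both arms. Power to detect p against 2p, two-sided 0.05, is Φ{[p − 1.96·√(2·m(1 − m)/50)] / √([p(1 − p) + 2p(1 − 2p)]/50)} with m = 1.5p:

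| Assumed p | Events per arm | No event in 100 | Power for a doubling |
|---|---|---|---|
| 0.5% | 0.25 | 61% | 5% |
| 1% | 0.5 | 37% | 6% |
| 2% | 1.0 | 13% | 8% |
| 5% | 2.5 | 0.6% | 15% |
| 8% | 4.0 | under 0.1% | 23% |

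The normal approximation is rough at such counts. The lower rows illustrate a broader definition that admits more events. Power is low throughout.

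**The case against.** **The bleeds are not lost.** A reader might infer that serious wound bleeds escape the safety analysis. They do not: each is counted in any bleeding, non-major bleeding and the wound composite, and a reoperated or fatal one is major. A general difference in wound bleeding has its own outcome. What stands is narrower: no listed outcome isolates the wound bleed that meets a threshold without reoperation.

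**The transfusion reading is not certain.** A reader might take it as settled that a wound bleed needing several units is non-major. The punctuation leaves room for the other reading, under which it is major. Only the hemoglobin limb is secure. This weakens the claim but is itself a reason to reword the sentence, because two assessors could classify the same bleed differently.

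**The restriction may be deliberate.** Surgery itself lowers hemoglobin and leads to transfusion, and keeping the wound out of these criteria limits that noise. With the unequal opening of the windows, it also gives some protection against a biased comparison. This objection stands. It is why the main definition should not be replaced, and why an added outcome needs its own window.

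**The numbers do not show that the safety conclusion is wrong.** One could point out that 0 events in 50 leaves an exact two-sided 95% upper bound of 1 − 0.025^(1/50) = 7.1%, and infer that a few wound bleeds would dominate the result. That bound follows from the assumed 50 per arm and is the same for any definition with no events. Without bleeding rates, the documents do not support a claim about how much the conclusion would change.

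**Conclusion.** The point holds in limited form. The hemoglobin threshold excludes surgical-site bleeding on either reading, and the transfusion threshold does so on the more natural one. Threshold-meeting wound bleeds managed without reoperation therefore cannot be separated from milder ones when the arms are compared.

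The number of such events is unknown. The figure of 2 percentage points per event rests on 100 patients and 1:1 allocation. The trial will be imprecise on bleeding under any definition, so the gain is visibility of serious wound bleeding and a definition that can be applied consistently, not adequate power. The documents do not show that the stated definition is invalid. This is a worthwhile improvement rather than a necessary correction.

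**What to change.** 1. Reword the major-bleeding sentence so that it states, for the hemoglobin criterion and the transfusion criterion separately, whether surgical-site bleeding is covered.
2. Keep the stated definition as the main safety outcome. Pre-specify one supplementary outcome: stated major bleeding plus clinically overt surgical-site bleeding that meets the same 2 g/dL or 2-unit threshold.
3. Count the supplementary outcome in both arms over the same postoperative window. It should open at a fixed time after the end of surgery, not at the first dose, and hemoglobin falls should be measured from a postoperative reference value.
4. Report it by arm with exact confidence intervals beside the main result.

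**Cost.** Hemoglobin and transfusions must be recorded for wound bleeds too, with a rule for the reference value; the plan's laboratory monitoring names only creatinine and platelets. Residual operative loss may still raise the counts, which is why the outcome stays supplementary. Treatment, sample size and the main safety outcome do not change.

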It is proposed to randomly assign at least 100 patients sequentially based on admission; in a single blind, interventional trial, to two separate groups. Patients are going to be selected from our university teaching hospital. patients were randomly assigned to a study group with the use of permuted blocks and stratification using well trusted randomization websites or software programs (SAS). Permuted block randomization list will be transferred from alphabetic symbol by the competent orthopedic supervisor and coded based on the randomization order by manual coding preset by orthopedic supervisor [5]. Double dummy technique may be feasible here as long as we tackled difficulty of providing syringes containing saline. However, the risk of injecting a saline solution subcutaneously (i.e. bleeding complications may develop in persons taking an anticoagulant agent plus unnecessary injections) may outweigh the benefit. Since the investigator do not know which therapy is administrated, the potential for the results to be biased is minimized [6].

The first group is to be on rivaroxaban with dosage according to the orthopedic approved regimen (10 mg once daily 6-10 hours after the surgery; recommended total duration of therapy: 12 to 14 days; ACCP recommendation: Minimum of 10 to 14 days; extended duration of up to 35 days suggested (Guyatt 2012).[3]

The other group will be administered the standard of care (SOC) enoxaparin. Dosage and duration of therapy are illustrated in Table 1 [2].

Drug	Dosage and Duration
Enoxaparin	Once-daily dosing: 40 mg once daily, with initial dose within 9 to 15 hours before surgery, and daily for at least 10 days (or up to 35 days postoperatively) or until risk of DVT has diminished or the patient is adequately anticoagulated on warfarin. The American College of Chest Physicians recommends initiation ≥ 12 hours preoperatively or ≥ 12 hours postoperatively; extended duration of up to 35 days suggested (Guyatt, 2012).

Table 1: *Dosing of SOC drugs used in thromboprophylaxis after orthopedic surgery.*

It is expected here that all medication will be taken for a duration of 10 days after surgery. The type, duration and dose of the thromboprophylactic agents will be discussed with and determined by the competent physician before saying a particular patient can be enrolled.

Study population

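### One secondary safety outcome starts its clock at the first rivaroxaban dose, so it has no valid count in the enoxaparin arm, and its end rule is ambiguous

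*Combined protocol and SAP*

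**What the plan says.** The document is a combined protocol and SAP. Under 'Outcome measure and follow up', the main safety outcome is "major bleeding beginning after the first dose of the study drug and up to 2 days after the last dose of the study drug (on-treatment" (the bracket names this the on-treatment period). The next list begins "Other safety outcomes include any on-treatment bleeding" and goes on to on-treatment non-major bleeding and haemorrhagic wound complications. It then adds a separate item: "any bleeding that starts after the first oral dose of rivaroxaban and ended up to 2 days after the last dose is administered".

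Under 'Study design and randomization', one group takes rivaroxaban, "10 mg once daily 6-10 hours after the surgery". For the comparator: "The other group will be administered the standard of care (SOC) enoxaparin". Table 1 gives enoxaparin once daily "with initial dose within 9 to 15 hours before surgery", and also cites a guideline start of at least 12 hours before or at least 12 hours after surgery. On blinding, the section says "Double dummy technique may be feasible here as long as we tackled difficulty of providing syringes containing saline", then warns that the risk of saline injections may outweigh the benefit. It describes no oral placebo. On duration: "It is expected here that all medication will be taken for a duration of 10 days after surgery".

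**The concern.** A safety outcome in a two-arm trial needs a start point that every patient can reach. This one names the drug of a single arm. An oral start point could serve both arms if the control group took a dummy tablet and the text said so, but the plan provides for neither. Tabulated by arm, the item would set rivaroxaban bleeds against a structural zero. Alternatively, an analyst would have to choose a substitute start point for enoxaparin, possibly after seeing the data.

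The end condition raises a second question. The main safety outcome classifies a bleed by when it begins. This item says when it ended. If that is meant literally, a bleed that starts on treatment and has not resolved by the cut-off is not counted.

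The plan's own background complains that bleeding has no standardised definition and that rivaroxaban's safety cannot be accurately compared with that of injectable anticoagulants. An outcome that only one arm can satisfy does not help with that.

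**Working it through.** The plan gives no figure that depends on this definition, so there is none to reproduce. The check compares the wording with the treatment plan, then gives illustrative sizes.

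**1. Can each arm meet the start condition?**

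| Outcome | Start point | Rivaroxaban arm | Enoxaparin arm |
|---|---|---|---|
| Major bleeding; any on-treatment bleeding; on-treatment non-major bleeding | first dose of study drug | reachable | reachable |
| The item in question | first oral rivaroxaban dose | reachable | never reached |

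No alternative start point is given for enoxaparin. An oral placebo, had one been adopted, would still not be a dose of rivaroxaban.

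**2. Size of the structural zero.** The plan randomises at least 100 patients to two groups; equal allocation (assumed) gives about 50 per arm. Assume the same true rate in both arms, 2% to 10%; the documents give no rate.

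- Rivaroxaban: 0.02 × 50 = 1 to 0.10 × 50 = 5 bleeds
- Enoxaparin: 0 by definition

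For scale, the two-sided Fisher p-value for 5/50 against 0/50 is 2 × C(50,5)/C(100,5) = 0.056. For 6/50 against 0/50 it is 2 × C(50,6)/C(100,6) = 0.027.

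**3. The literal end rule.** The cut-off is last dose plus 2 days: 10 + 2 = day 12 on the expected course. The same section also mentions 12 to 14 days and up to 35 days, which would put it at day 14 to 16 or up to day 37.

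To see how many bleeds such a rule might drop, take a window of T = 12 − 8/24 = 11.67 days (first rivaroxaban dose at 8 hours, mid-range) and exponential bleed durations with mean d. With onset uniform over the window, the share still unresolved at the cut-off is (d/T)(1 − e^(−T/d)). The early-onset column was simulated, with exponential onset (mean 3 days) truncated to the window. Onset patterns and durations are assumptions.

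| Mean duration d (days) | Dropped, uniform onset | Dropped, early onset |
|---|---|---|
| 1 | 9% | 1% |
| 2 | 17% | 4% |
| 3 | 25% | 8% |
| 5 | 39% | 20% |

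In these runs the dropped bleeds lasted on average about 2 to 4 times as long as those counted.

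**4. Would it be enough to substitute the first dose of study drug?** Measure from surgery, with the window closing at 12 × 24 = 288 h.

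- Rivaroxaban opens at +6 to +10 h: 288 − 6 = 282 h down to 288 − 10 = 278 h
- Enoxaparin with a preoperative start opens at −15 to −9 h: 288 + 15 = 303 h down to 288 + 9 = 297 h

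The enoxaparin window opens 6 + 9 = 15 h to 10 + 15 = 25 h earlier and includes the operation. The substitution would make the item computable in both arms, but the windows would differ and the item would largely repeat any on-treatment bleeding. A clock that starts at the end of surgery gives both arms the same start.

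**The case against.** The strongest reply is that little depends on this item. It is one entry in a list of other safety outcomes, and 'Data analysis' names no specific test for it. Three bleeding outcomes already use a window that applies to both arms. That stands. A reader might infer from the faulty wording that the trial cannot compare bleeding between rivaroxaban and enoxaparin; the documents do not support this, because the main safety outcome is unaffected.

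A second reply is that 'ended' may be loose English for the end of the observation window, since the phrase closely follows the main outcome's wording. That is plausible, and it would remove the second defect but not the first. A reader might also infer that the rule discards the longest bleeds. Even the literal text does not say so. It drops bleeds unresolved at the cut-off, which includes short bleeds that start late, and it keeps a long bleed that starts early and resolves in time. Longer bleeds are only more likely to be lost.

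Third, the plan does not firmly reject a double dummy; it says the risk of saline injections may outweigh the benefit. That is true, but no dummy is adopted.

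Finally, the item may have been meant as a description of the rivaroxaban arm alone. If so, the text should say so; at present it stands unqualified among the trial's safety outcomes.

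**Conclusion.** The point holds, within limits. As written, the item yields zero or undefined events in the enoxaparin arm and cannot compare the arms. This follows from the text and needs no assumption. The end rule is ambiguous, and if literal it excludes bleeds unresolved 2 days after the last dose.

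The sizes are illustrations only. The 1 to 5 against 0 rests on about 50 patients per arm and an assumed 2% to 10% rate. The share lost to a literal end rule rests on assumed onset patterns and durations.

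The wording should be corrected before any bleeding data are tabulated. It does not threaten the main safety comparison.

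**What to change.** Replace the item with one onset-based rule for both arms: *any bleeding that starts after the end of surgery and no later than 2 days after the last dose of the assigned study drug, whether or not it has stopped*. If a surgery-anchored outcome is not wanted, delete the item, because re-anchoring it to the first dose of study drug would largely duplicate any on-treatment bleeding.

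The cost is one sentence, plus recording the times of bleed onset and end of surgery, which the documents do not say are collected. The new window also takes in some early postoperative bleeds that occur before the first rivaroxaban dose. The text should state this, so that the outcome is read as bleeding after surgery under each assigned strategy.

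The start should not be delayed to, say, 6 hours after surgery on the view that earlier bleeds are caught by any on-treatment bleeding. On the plan's timings a rivaroxaban bleed in those hours precedes the first dose and would fall in neither outcome. An enoxaparin bleed at the same time is on-treatment if the first dose was preoperative. The gap would differ by arm.

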For patients with suspected high-risk PE with shock or hypotension, emergency computed tomography(CT) angiography beside transthoracic echocardiography is recommended depending availability and clinical circumstances. While for patients not suspected of having high-risk PE, clinical assessment of likelihood of PE using validated prediction rules and clinical judgement to distinguish between low and high-risk PE may use [8]. However, PE can be diagnosed based on computed tomography pulmonary angiography (CTPA). CT pulmonary angiography is preferred method when available.

It is recommended to have baseline Scr and platelets count. Based on Heparin induced thrombocytopenia, it is advisable to monitor platelets count beginning of the fourth day and every three days until discontinue of Heparins.

Data analysis

The patients in the two groups will be matched in advance for the difference in Patients’ characteristics, VTE risk factors, history of VTE, types of surgery, types of anesthesia and duration of surgery. This ensures fair randomization between groups. Statistical analysis will be performed at an overall significance level of 0.05, adjusted for the primary and secondary end points using non- independent t-test

(SPSS software). Comparisons of the primary end points between treatment groups were performed by means of a log-rank test. To estimate the size of the effect, we will use a Cox regression model. On the other hand, the cost-effective analysis (CEA) will be based mainly on estimating the average cost-effective ratio(ACER) and the incremental cost for each additional cure.

References

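### The plan gives three accounts of how a patient's arm is set (a permuted-block list, a physician's decision on the agent, and advance matching on six factors) and does not reconcile them

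*Combined protocol and SAP*

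**What the plan says.** The combined protocol and SAP describes allocation in two sections.

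**Study design and randomization.** The plan is to "randomly assign at least 100 patients sequentially based on admission", and it adds that "patients were randomly assigned to a study group with the use of permuted blocks and stratification". Strata, block size and allocation ratio are not given. Protection against bias is said to follow from masking: "Since the investigator do not know which therapy is administrated". The section closes with a different statement, set as a step that precedes enrolment: "The type, duration and dose of the thromboprophylactic agents will be discussed with and determined by the competent physician before saying a particular patient".

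**Data analysis.** This section opens with "The patients in the two groups will be matched in advance" and lists six items: patient characteristics, VTE risk factors, VTE history, and then "types of surgery, types of anesthesia and duration of surgery. This ensures fair randomization between groups". Next, the 0.05 significance level is to be "adjusted for the primary and secondary end points using non- independent t-test". The following sentence reads "Comparisons of the primary end points between treatment groups were performed by means of a log-rank test". A Cox model is to estimate the size of the effect.

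Study population also bears on the point. It enrols patients scheduled for surgery for whom prophylaxis has already been decided on. It does not say that the choice between the two drugs has been made.

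**The concern.** Random allocation is what lets a difference between rivaroxaban and enoxaparin be attributed to the drug. A reader who follows the text literally finds more than one rule for setting the arm, and the consequences differ:

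- If the list alone operates, the comparison is sound. The harm is misleading text and a paired test applied to unpaired groups.
- If the physician's decision on the agent operates, the arm can follow perceived thrombosis or bleeding risk. Both the efficacy and the safety comparisons are then confounded, and a larger sample does not remove that.
- If the groups are assembled by non-random matching, the six listed factors may be balanced, but unmeasured ones are not protected.
- If randomised pairs were meant, protection against unmeasured factors is kept, but the pairing rule and a matched analysis for event data are missing.

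The documents do not say which of these applies.

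**Working it through.** No stated figure is in dispute, so the check is mainly a comparison of the sections.

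**1. List against physician.** The trial has two drugs, one per arm. A permuted-block list fixes the drug from the order of entry (and the stratum). A decision on the type of agent taken before enrolment fixes it from the patient. Both cannot set the arm. No sentence limits the physician to eligibility, or says that the code is opened after the physician's decision.

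**2. List against matching.** Patients enter one at a time by admission. The two groups do not exist beforehand, so they cannot be matched beforehand. The inference drawn from matching also runs the wrong way: randomisation rests on chance assignment, and matching neither creates nor secures it.

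**3. Timing.** Assignment is by admission. Table 1 includes a first enoxaparin dose 9 to 15 hours before surgery, so under that option the arm must be known at least 9 hours beforehand. Table 1 also cites a postoperative start, but admission still comes before surgery. Actual duration of surgery is therefore unknown when the arm is set. A planned duration could be known, but the text does not say planned.

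**4. Could matching mean stratification on these factors?** This is the closest benign reading. As an illustration, assume 100 patients and two equally likely levels per factor (the levels are not in the documents). With *k* factors there are 2^k strata, 100/2^k patients per stratum on average, and the chance that a stratum holds fewer than 4 patients is the binomial P(X < 4) with n = 100 and p = 1/2^k.

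| Factors | Strata | Mean per stratum | P(fewer than 4) |
|---|---|---|---|
| 2 | 4 | 25.0 | 0.000 |
| 3 | 8 | 12.5 | 0.001 |
| 5 (without duration) | 32 | 3.1 | 0.619 |
| 6 | 64 | 1.6 | 0.928 |

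So stratifying on all six is impractical at about 100 patients as well as impossible for actual duration. Two or three factors would be workable. The text names none.

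**5. Paired test against log-rank.** A non-independent t-test analyses within-pair differences. No pairs are defined anywhere. The log-rank test in the next sentence, as named, compares two independent groups. The t-test sentence covers primary and secondary endpoints and the log-rank sentence only the primary ones. Deleting the t-test without a replacement would leave the secondary endpoints with no explicitly named test.

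**6. Size of any bias.** The documents give no event rate, no share of high-risk patients and no indication of how a physician would choose. Neither the size nor the direction of a bias can be derived from them.

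**The case against.** The other side has a good case. Random assignment is stated twice, with permuted blocks, stratification, named software and an investigator unaware of therapy. The physician sentence speaks of agents in the plural, groups type with duration and dose, follows regimens given partly as ranges, and ends with enrolment. It reads naturally as a check before entry, which agrees with Study population. The matching sentence may be a loose description of stratification or of a baseline table. Randomised pairs are also possible: no block size is given, and blocks of two within strata would make both the matching and the paired test coherent.

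Much of this stands. The list is the likeliest mechanism, and physician choice is the weaker reading. A reader might infer that the trial is not really randomised, or that its result is already confounded. The documents do not support that; they show conflicting wording, not how allocation is done. A reader might also want to attach a spurious risk ratio to physician choice. Any such figure would rest wholly on assumed inputs, so it cannot support the seriousness of the point. The unsuitability of a t-test for an event endpoint is a separate matter that holds under any allocation method, and it is not evidence of non-random allocation.

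What does not stand is that the benign readings settle the text. None of them is written down. Stratification, a list and randomised pairs all fail to accommodate actual duration of surgery. A baseline table could include it, but would be neither done in advance nor a guarantee of fair randomisation.

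**Conclusion.** The point holds as an internal contradiction within Study design and randomization, and between that section and Data analysis, over how the arm is set, with a paired test that fits neither the described allocation nor the log-rank comparison. Confidence is high that the wording conflicts. It does not extend to a claim that allocation is non-random. The size of any bias cannot be estimated; if only the list operates, there is no allocation bias from this source. The conclusion assumes only that *type* means which drug and that duration of surgery means its actual length. This should be fixed, because following the text literally would either pre-empt the list or apply the wrong test.

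**What to change.** Reconcile the two sections.

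- **Allocation.** State that the arm comes only from the permuted-block list, and that the code is opened after the physician has confirmed that the patient is eligible and suitable for either arm. Remove the type of agent from the physician's decision before enrolment. The sponsor should also state how the remaining wording on duration and dose fits with the protocol regimens.
- **Matching.** Delete the statement that groups are matched beforehand and the claim that this secures fair randomisation. Report the six factors descriptively by arm, with duration of surgery as a perioperative variable.
- **Stratification.** State when randomisation occurs. Name the factors actually used, limited to a few known at that time, and account for them in the log-rank and Cox analyses where event numbers allow.
- **Tests.** Replace the paired t-test for comparisons between arms with unpaired methods: log-rank and Cox for the primary endpoint, and likewise, or an unpaired comparison of proportions, for the secondary endpoints.
- **If randomised pairs were intended,** say so, define the pairs on factors known before surgery, and use a matched analysis suited to event data.

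The cost is protocol wording, plus a new list if the named strata differ from those used. No patients or visits are added. The downsides are sparse strata with about 100 patients if too many factors are chosen, and possible chance imbalance on factors left out.
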